8.2.3 Other Analyses

The following Basic Results Tables will also be produced for the final study report:

- Baseline Characteristics in safety analysis set
- Summary of Baseline Characteristics in safety analysis set
- All Adverse Events in safety analysis set
- Summary of Each SOC/PT of Adverse Events in safety analysis set
- Summary of Effectiveness Evaluation in effectiveness analysis set
- Subjects Flow Chart (the number of subjects who started the study, the number of subjects in safety analysis set, the number of subjects in effectiveness analysis set)

9 APPENDICES

9.1 APPENDIX 1: NOTES

- Each statistical analysis will be carried out with SAS Software version 9.4 or more recent version.
- Ambiguous data such as “ ≥ 20 ”, “ > 20 ” will be excluded from analysis.

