7.2.4.2. Demography and Baseline Characteristics

The following will be recorded on the CRF for each subject:

- Age: Record the age of the subject at the time of enrollment. The age should be calculated by the date of birth.
- Purpose of treatment: Between 'treatment for moderate to severe vasomotor symptoms associated with menopause' and 'prevention of post-menopausal osteoporosis', select one that is applicable, but both can be selected.
- Presence and characteristics of the vasomotor symptoms associated with menopause: Select 'Yes' or 'No'. If 'Yes' is selected, select 'moderate' or 'severe' for the severity and record the duration of the disease (years/months).
- Other past/present diseases: Past or present diseases (including liver disorder and renal disorder) will be determined based on the date of the first dose of Duavive tab. Record 'Yes' or 'No'. If 'Yes', record the adequate full name of the disease as specified in the Medical Terminology Dictionary (published by the Korean Medical Society), and indicate whether it is 'Past disease' or 'Present disease'. 'Past disease' refers to a disease occurred in the past of which the condition has been recovered by the time of the administration of Duavive tab., whereas 'Present disease' refers to a disease that is present at the time of the first administration of Duavive tab.
- Allergic history: Record the history of all allergies.

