6.2 EFFECTIVENESS ENDPOINT(S)

- 1) Treatment for moderate to severe vasomotor symptoms associated with menopause: Investigator’s judgment on the improvement of the symptom recorded during the treatment

2) Prevention of post-menopausal osteoporosis:

- The investigator's evaluation of preventive effect based on this information.
- Laboratory test results (if any)
 - X-ray examination
 - Bone density test record (Bone mineral density)
 - Other blood test record related to resorption of bone and osteogenesis (Biochemical marker of bone turnover)

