7 HANDLING OF MISSING VALUES

No imputation of missing data will be performed. Missing or incomplete dates will be excluded from the analysis.

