8.2 STATISTICAL ANALYSES

8.2.1 Safety Analyses

8.2.1.1 Baseline Characteristics

Baseline characteristics for this study are defined as follows:

- Continuous measurements will be presented Mean (SD) :
 - Age
 - Duration of disease[†]
 - Total administration period of Duavive tab.[‡]
- Categorized measurements will be presented n(%) :
 - Main indication (Treatment for moderate to severe vasomotor symptoms associated with menopause, Prevention of post-menopausal osteoporosis, both)
 - Geriatric status (<65 years, ≥65 years)
 - Age (<50 years, ≥50 years and ≤59 years, ≥60 years and ≤69 years, ≥70 years*)
 - Allergy history (Yes, No)
 - Duration of disease[†] (<3 months, ≥3 months and <6 months, ≥6 months*)
 - Medical history (Past disease, Present disease/Yes, No)
 - Total administration period of Duavive tab. (<3 months, ≥3 months and <6 months, ≥6 months*)
 - Long-term administration (<22 weeks, ≥22 weeks of total administration period of Duavive tab.)
 - Kidney disorder (Yes, No)
 - Liver disorder (Yes, No)
 - Concomitant medication (Yes, No)
 - Hormone therapy related to menopause before administration of Duavive Tab. (Yes, No)

[†] Only if main indication is “Treatment for moderate to severe vasomotor symptoms associated with menopause”

Duration of disease (months) = (number of years after diagnosis)×12+(number of months after diagnosis)

[‡] Total administration period of Duavive tab.= Sum of each administration period

: Each administration period = (Administration end date) – (Administration start date) + 1

If the medication is being continued at the completion of the study, administration end date is replaced with effectiveness evaluation date at last visit.

* The categories can be altered depending on the data distribution.

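### SAP 9.1 discards values recorded with a bound, such as ≥20, even when the bound already settles the category needed (minor)

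*SAP*

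**What the plan says.** The note in SAP 9.1 gives ≥20 and >20 as examples of ambiguous data and states that such data "will be excluded from analysis". It names no variable, allows no exception and asks for no count of what is removed. SAP 7 adds "No imputation of missing data will be performed", so a discarded value is not recovered elsewhere.

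Two kinds of planned variable can carry a bound:

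- **Duration of vasomotor symptoms.** Protocol 7.2.4.2 asks the investigator to "record the duration of the disease (years/months"). SAP 8.2.1.1 converts this to months with "Duration of disease (months) = (number of years after diagnosis)×12+(number of months after diagnosis"), which needs exact numbers. The planned categories are under 3 months, then "≥3 months and <6 months, ≥6 months". A footnote adds "The categories can be altered depending on the data distribution".
- **Bone laboratory results.** SAP 6.2 lists among these "Other blood test record related to resorption of bone and osteogenesis (Biochemical marker of bone turnover"), and SAP 8.2.2 compares last-visit values with baseline where they exist.

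Duration is one of the categorised characteristics used to split adverse events (SAP 8.2.1.3) and vasomotor effectiveness (SAP 8.2.2). SAP 8.1.2 makes the analysis set the denominator for percentages.

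**The concern.** A bounded entry carries partial information, and for a categorical summary partial information can be enough. An entry of ≥20 cannot be turned into an exact number of months, but it cannot belong below 6 months in either unit. Discarding it loses an observation whose category is certain and, for lower bounds, takes it only from the top row.

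Elsewhere the SAP follows the opposite principle. In SAP 8.2.1.2 an adverse event with a partial onset date counts as on-treatment unless the known month and year place it before the first dose. What is known is used when it settles the classification.

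At stake are the duration table and the duration rows of the factor tests, which serve the second study objective (finding factors that affect safety and efficacy). To a lesser degree the bone laboratory comparison is affected too, because a pair is lost if either of its members carries a bound.

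**Working it through.** The documents give no count of bounded values and no figure to reproduce. Every share and distribution below is an assumption.

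**1. Is the category certain?** The cut-points are 3 and 6 months. ≥20 months exceeds 6, and ≥20 years = 240 months or more also exceeds 6. So the category is certain under the planned cut-points. This is not true of every bound: >2 months could fall in any of the three categories.

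**2. Effect on the top-category share.** Let p be the true share at 6 months or more, and b the share of women with an entry such as ≥20, all of whom belong in that category. The denominator is the women to whom duration applies.

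- Among usable values: (p − b)/(1 − b)
- With the full-set denominator of SAP 8.1.2: p − b

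Per 100 women with p = 70% and b = 10%, 70 belong in the top row and 10 are discarded. That leaves 60 of 90 usable values = 66.7%, or 60 of 100 = 60%. Keeping the 10 gives (60 + 10)/100 = 70%, the true share.

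| Assumed p | b = 1% | b = 5% | b = 10% | b = 20% |
|---|---|---|---|---|
| 50% | 49.5 / 49 | 47.4 / 45 | 44.4 / 40 | 37.5 / 30 |
| 70% | 69.7 / 69 | 68.4 / 65 | 66.7 / 60 | 62.5 / 50 |
| 90% | 89.9 / 89 | 89.5 / 85 | 88.9 / 80 | 87.5 / 70 |

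(Per cent of usable values / per cent of the full set.)

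**3. Does the direction hold for other bounds?** Simulation with 2,000,000 draws, duration log-normal, median 18 months, log-SD 1. With nothing excluded, the mean is 29.7 months and the share at 6 months or more is 86.4%.

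- 10% of values ≥20 recorded as bounds and dropped: mean 28.6, share 85.8%.
- 50% of values <3 recorded as bounds and dropped: mean 30.2, share 88.1%.
- Both together: mean 29.1, share 87.5%. The mean falls while the share rises.

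In this distribution 20 months is at Φ(ln(20/18)) = Φ(0.105), about the 54th percentile, so it is not an extreme value.

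**4. Paired bone marker.** Assume unit SD at both times, correlation 0.6, true mean change −0.50 and reporting limits 1.5 SD above and below the baseline mean. Write the follow-up value as −0.50 + u, with u standard normal.

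- Baseline above the upper limit dropped: −0.50 + (0.6 − 1) × (−φ(1.5)/Φ(1.5)) = −0.50 + 0.4 × 0.139 = −0.44.
- Follow-up below the lower limit dropped (u < −1): −0.50 + 0.4 × φ(1)/Φ(1) = −0.50 + 0.4 × 0.288 = −0.38.
- Follow-up above the upper limit dropped (u > 2): −0.50 − 0.4 × φ(2)/Φ(2) = −0.50 − 0.4 × 0.055 = −0.52.

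The first two shrink the apparent fall and the third enlarges it.

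**5. What the rule cannot touch.** Age comes from date of birth and the administration period from dates. The safety endpoint (SAP 6.1) is whether an adverse event occurred. The effectiveness rates (SAP 8.2.2) come from the investigator's categorical rating.

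**The case against.** The strongest reply is that little depends on this note. The main interest is adverse event frequency (Protocol 7.7.2), which the rule cannot alter. The SAP has no hypotheses. Duration is one baseline descriptor, defined only for the vasomotor indication, and bone tests are collected only where routine practice supplies them. Protocol 7.6 sends data needing review back to the site as queries, so a vague duration may be made exact before the note applies. The duration cut-points may also change. All of this stands, and it limits the severity. It does not justify discarding an entry that remains bounded after querying, and a query cannot resolve an assay limit.

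A reader might also infer more than the documents support:

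- *That only extreme values are removed.* The note concerns imprecise recording, and a bound need not lie in a tail (step 3).
- *That every summary is biased in a known direction.* This holds for one-sided bounds such as the SAP's two examples. It fails for a mix of < and > entries and for change from baseline (steps 3 and 4).
- *That women are dropped from the study results.* A bounded entry is not among the exclusions in SAP 5.1 or 5.2. The woman stays in her analysis set and in every other factor test, and only that value is lost.

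**Conclusion.** The point holds in a narrow form and is minor. Under the planned cut-points the SAP discards duration entries whose category is certain. For lower bounds such as its own examples, this understates the share at 6 months or more and thins that row in the factor tests. With an assumed true share of 70% and 10% of women with bounded entries, the reported share is 66.7% or 60%, depending on the denominator. At 1% bounded it is 69.7% or 69%. The real size is unknown because the frequency of bounded entries is not given. Bone laboratory pairs may also be lost, with no general direction of bias. Overall adverse event incidence and overall effectiveness rates are unaffected.

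**What to change.** Replace the note in SAP 9.1 with wording such as:

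> A value recorded with a bound is assigned to its category whenever the bound determines that category under the final cut-points. It is excluded from means and SDs. The number and direction of bounded values are reported for each variable, including laboratory results at assay limits.

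This is compatible with the no-imputation rule in SAP 7, because no value is invented and only the category already known is used. Keeping a bounded value at its bound in the mean would be single-value substitution. That would conflict with SAP 7 and is not proposed. Where SAP 8.1.2 uses the full-set denominator, entries that still cannot be classified should have their own row, so that the percentages add to 100.

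The cost is a short SAP edit and minor programming. The categorical and continuous summaries of duration may then have different n, which a table footnote can explain. The true mean of a variable with bounded values remains unrecoverable, but the reported counts will show how far that matters.
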